2.8.2 Deaths

Any deaths up to and including Week 24 will be included in a separate AE table by treatment group for Week 24 analysis summarizing fatal events. Additional deaths in Epoch 4 will be included in a separate AE table similarly for the End of study analysis.

Deaths will also be listed by treatment groups for both Week 24 analysis and End of study analysis.

2.8.3 Laboratory data

Table 2-4 Laboratory data

Category	Parameter(s)
Hematology	RBC (total), WBC (total), platelet count (direct), hemoglobin, hematocrit, basophils (absolute, %), eosinophils (absolute, %), lymphocytes (absolute, %), monocytes (absolute, %), neutrophils (absolute, %)
Biochemistry	ALT, albumin, alkaline phosphatase (ALP), AST, bicarbonates, bilirubin (direct, total), blood urea nitrogen (BUN), calcium (total), chloride, creatinine, cystatin C, eGFR (MDRD), magnesium, phosphates, potassium, protein (total), sodium, uric acid, γ -GT, amylase, lipase
Urinalysis	pH, specific gravity, protein, glucose, ketones, nitrites, blood, leucocytes, Urine albumin to creatinine ratio (spot urine)

All laboratory samples will be processed through the central laboratory. Laboratory data consist of hematology, clinical chemistry, and urinalysis.

Hematology data are collected at Visit 1, 201, 205, 299/301, 302, 303, and 399; clinical chemistry data are collected at Visit 1, 201, 203, 205, 299/301, 302, 303, and 399; and Urinalysis are collected at Visit 201, 205, 299/301, 303, and 399.

Week 24 analysis

Descriptive summary statistics including for the change from BL to each study visit up to and including Week 24 visit will be presented by treatment group for each laboratory parameter, as well as for the maximum change from BL. In addition, shift tables will be provided for all parameters with available ranges to compare a subject's BL laboratory evaluation relative to the most extreme post-BL value. For the shift tables, normal ranges as well as specifically defined clinically notable/abnormality limits, if available – will be used.

A listing of all patients with notable laboratory values will be provided.

Urinary calcium and phosphorus excretion will be collected for a subset of subjects participating in the PK analysis. The change from BL in the 24-h urinary calcium and phosphorus excretion will be descriptively summarized by treatment and visit.

Clinically notable laboratory abnormalities for selected tests based on a percent change from baseline are shown in Table 2-5.

Table 2-5 Clinically notable laboratory abnormalities for selected tests

Parameter	Criteria (based on a percent change from baseline or change from baseline)
Hematology	
RBC (total)	>50% increase, >20% decrease
WBC (total)	>50% increase, >50% decrease
Platelet count	>75% increase, >50% decrease
Hemoglobin	>50% increase, >20% decrease
Hematocrit	>50% increase, >20% decrease
Clinical chemistry	
ALT	>150% increase
AST	>150% increase
BUN	\geq 50% increase
Creatinine	\geq 50% increase
Total bilirubin	>100% increase
ALP	>100% increase
Sodium	>5% increase, >150 mmol/L, <130 mmol/L
Potassium	absolute values < 3.0 mmol/L, > 5.9 mmol/L
Chloride	>10% increase, >10% decrease
Calcium	>10% increase, >10% decrease, hyper > 2.6 mmol/L
Uric acid	>50% increase
Plasma glucose	>50% increase
Plasma glucose	< 3.0 mmol/L (54 mg/dL)

End of study analysis

Descriptive summary statistics including for the change from Week 24 to each post-Week 24 study visit during Epoch 4 will be presented by treatment group for each parameter, as well as for the maximum change from BL. In addition, shift tables will be provided for all parameters with available ranges to compare a subject's Week 24 laboratory evaluation relative to the most extreme post-Week 24 value.

The change from Week 24 in the 24-h urinary calcium and phosphorus excretion will be descriptively summarized by treatment and visit (for post-Week 24 visits only) for a subset of subjects participating in the PK analysis.

A listing of all patients with notable laboratory values will be provided as well.

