## Glossary of terms

Baseline (BL)	Randomization (Visit 201) will be considered BL in this study.
Dosage	Dose of the study treatment given to the subject in a time unit (eg 25 mg once a day, 50 mg twice a day (bid),...).
Electronic data capture (EDC)	EDC is the electronic acquisition of clinical study data using data collection systems, such as Web-based applications, interactive voice response systems and clinical laboratory interfaces. EDC includes the use of electronic case report forms (eCRFs) which are used to capture data transcribed from primary sources used at the point of care.
End of study analysis	Statistical analyses performed at the end of the study including those specified in the statistical analysis plan and any data driven analyses that are performed at study end. The end of study analysis will take place after the last subject has completed Epoch 4 at Week 48.
Enrollment	Time of subject entry into the study at which the informed consent must be obtained (eg prior to starting any of the procedures described in the protocol). In this protocol, this will be at Visit 1 in Epoch 1.
Epoch	A portion of the study which serves a specific purpose. In this study, the 4 epochs are: screening, run-in, randomization & treatment, and follow-up.
eSource	eSource direct data entry refers to the capture of clinical study data electronically, at the point of care. eSource platform/applications reduce the use of paper capture source data during clinical visits. eSource combines source documents and case report forms into one application, allowing for the real time collection of clinical study information to sponsors and other oversight authorities, as appropriate.
Investigational drug	The drug of which the properties are being tested in the study; this definition is consistent with United States code of federal regulations (CFR) 21 Section 312.3 and is synonymous with “investigational new drug” or “investigational medicinal product”. In this study, the investigational drug is LIK066.
Medication pack number	A unique identifier on the label of each investigational drug package.
Randomization number	A unique identifier assigned to each randomized subject, corresponding to a specific treatment arm assignment (see Section 5.3 ).

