## 2.2 Secondary objective(s)

1. To assess the responder rates according to percent decrease in body weight either  $\geq 5\%$  or  $\geq 10\%$ , from BL at Week 24, for the overall population and each of the subgroups (normoglycemic subjects, dysglycemic subjects and subjects with T2DM, see [Section 9.5.1](#)).
2. To assess the dose-response relationship for weight loss in normoglycemic subjects, dysglycemic subjects and subjects with T2DM after 24 weeks of treatment (see [Section 9.5.1](#)).
3. To evaluate the effect of all LIK066 doses and regimens *vs* placebo (see [Section 9.5.1](#)) for the overall population and by subgroups (normoglycemic subjects, dysglycemic subjects and subjects with T2DM, see [Section 3.1](#)) after 24 weeks of treatment and between Week 24 and Week 48 on:
  - Waist circumference, see [Section 6.4.2](#).
  - Change from BL in glycated hemoglobin A1c (HbA1c), see [Section 6.4.3](#).
  - Change from BL in fasting plasma glucose (FPG), see [Section 6.4.4](#).
  - Changes in systolic blood pressure (SBP) and diastolic blood pressure (DBP), see [Section 6.4.5](#).
  - Changes in the fasting lipid profile and high sensitivity C-reactive protein (hsCRP, see [Section 6.4.6](#)).
  - 24-h urinary glucose excretion (UGE) in a subset of subjects (see [Section 6.4.7](#)).
4. To evaluate the change in weight and other efficacy parameters listed in #3 in the overall population and by subgroups by LIK066 treatment *vs* placebo (see [Section 9.5.1.2](#)) between Week 24 and Week 48 (in Epoch 4, see [Section 3.1.3](#)).
5. To evaluate safety (adverse events (AEs) and laboratory parameters) and tolerability of LIK066 over 24 weeks of treatment and over 48 weeks of treatment for all subjects (see [Section 9.5.2](#)).
6. To evaluate AEs of interest and laboratory data (see [Section 9.5.2.2](#)) in subjects treated with LIK066 25 mg qd, 35 mg qd or placebo between Week 24 and Week 48 (during Epoch 4).
7. To evaluate 24-h urinary calcium and phosphorus excretion after 24 weeks of treatment and after 48 weeks of treatment in a subset of subjects.
8. To evaluate the pharmacokinetics (PK) of LIK066 (see [Section 6.6.3](#) and [Section 9.5.4](#)).

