2.1.1 General definitions

Baseline (Week 0) for Week 24 analysis and overall analysis including both Epoch 3 and Epoch 4 data will be defined as the last measurement before or at the randomization visit. Baseline for End of study analysis including Epoch 4 data only will be defined as the last measurement in Epoch 3.

The first day of administration of randomized study treatment (first dose) is defined as Day 1 for the study. If the date of first administration is missing, then randomization date will be used as Day 1.

All other study days will be labeled relative to Day 1. For event dates on or after Day 1, study day for a particular event date is calculated as [Date of event] – [Date of first dose] + 1. For the dates before Day 1, study day for an event date is calculated as [Date of event] – [Date of first dose]. Duration of an event will be calculated as [Event end date] – [Event start date] + 1. The descriptor “Day 0” will not be used.

For Week 24 analysis, the treatment groups presented are:

- LIK066 2.5 mg qd
- LIK066 10 mg qd
- LIK066 50 mg qd
- LIK066 150 mg qd
- LIK066 2.5 mg bid
- LIK066 5 mg bid
- LIK066 25 mg bid
- LIK066 50 mg bid
- Placebo
- Total (if applicable)

For End of study analysis, unless specified otherwise, the following treatment grouping strategy will be used, expressed as per the Epoch 3 treatment/Epoch 4 treatments a subject is assigned to at randomization:

- LIK066 qd any dose/LIK066 25 mg qd, shortened as LIK066 qd/LIK066 25 mg qd
- LIK066 bid any dose/LIK066 35 mg qd, shortened as LIK066 bid/LIK066 35 mg qd
- Placebo/LIK066 25 mg qd
- Placebo/placebo, shortened as Placebo
- Total (if applicable)

For End of study AE listings, the 10 randomized treatments will be used, as shown in Section 1.1 study design, along with the additional two pooled groups:

- LIK066 qd any dose/LIK066 25 mg qd, shortened as LIK066 qd/LIK066 25 mg qd
- LIK066 bid any dose/LIK066 35 mg qd, shortened as LIK066 bid/LIK066 35 mg qd
- Total (if applicable)

For overall analysis including both Epoch 3 and Epoch 4 treatment, the 10 randomized treatment grouping strategy will be used, as shown in Section 1.1 Study design.

For the Week 24 analyses, data collected up to the end date of Epoch 3 will be included. For AEs and concomitant medications, this means that events with start dates prior to the end of Epoch 3 dates are included.

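### SAP 2.8.3 plans no laboratory shift, change-by-visit or notable-change analysis over Weeks 0-48 from the randomisation baseline, although secondary objective 5 covers laboratory parameters over 48 weeks

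*SAP*

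**What the plan says.** For the End of study analysis, SAP 2.8.3 plans descriptive statistics for the "change from Week 24 to each post-Week 24 study visit during Epoch 4", "as well as for the maximum change from BL". Its shift tables compare the "Week 24 laboratory evaluation relative to the most extreme post-Week 24 value". A listing of patients with notable values is planned, without naming the reference value. Urinary calcium and phosphorus are summarised as change from Week 24, at later visits only. Protocol 9.5.2.2 sets the same references for changes and shifts.

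SAP 2.1.1 states: "Baseline for End of study analysis including Epoch 4 data only will be defined as the last measurement in Epoch 3". In the same paragraph, baseline for the Week 24 analysis and the "overall analysis including both Epoch 3 and Epoch 4 data will be defined as the last measurement before or at the randomization visit". The protocol glossary has a single rule: "Randomization (Visit 201) will be considered BL in this study".

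The criteria column of SAP Table 2-5 is headed "Criteria (based on a percent change from baseline or change from baseline", although some rows carry absolute limits.

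Secondary objective 5 (Protocol 2.2) is to evaluate safety, naming adverse events and laboratory parameters, and "tolerability of LIK066 over 24 weeks of treatment and over 48 weeks of treatment for all subjects". SAP Table 1-1 gives change from baseline at both Week 24 and Week 48 as the urinary calcium and phosphorus endpoint.

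**The concern.** The SAP defines a randomisation baseline for an overall analysis of both epochs, but specifies such an analysis only for adverse events (SAP 2.8.1) and exposure (SAP 2.4.1). The laboratory half of objective 5 has no counterpart. For most subjects Week 24 is a value on LIK066, so a change measured from it describes the second 24 weeks and not 48 weeks of treatment.

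What is at stake is slow accumulation: a drift that is modest in each epoch but notable from randomisation. Protocol 3.6 reports red-cell decreases, increased calcium excretion and renal changes in animals, so these are parameters for which a 48-week view is wanted.

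**Working it through.** No power or alpha figure is involved. The check sets the passages side by side, then uses short arithmetic.

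**1. Which reference does each laboratory output use?**

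| Output | Week 24 analysis | End of study analysis | Weeks 0-48 from randomisation |
|---|---|---|---|
| Change by visit | Randomisation | Week 24 | Not specified |
| Shift to most extreme value | Randomisation | Week 24 | Not specified |
| Maximum change | Randomisation | BL, meaning unclear | Only if BL means randomisation |
| Table 2-5 percent flags | Randomisation | Not stated; last Epoch 3 value if SAP 2.1.1 applies | Not specified |
| Urinary calcium/phosphorus | Randomisation | Week 24 | Named in Table 1-1, not planned in 2.8.3 |

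The two shift tables cannot be added to give a 48-week count. A subject normal at randomisation, high at Visit 205, normal at Visit 299 and high at Visit 303 is a normal-to-high shift in both.

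**2. For whom is Week 24 an on-drug value?** SAP Section 3 gives 432 subjects in the ratio 1:1:1:1:1:2:1:1:1:2, which is 12 parts.
- 432 / 12 = 36 per part, matching the arms of 36 or 72 in Protocol 5.2.
- Eight LIK066 arms: 10 × 36 = 360, and 360 / 432 = 83.3%.
- Placebo: 2 × 36 = 72. For the 36 who then take 25 mg, Week 24 is a pre-drug value.

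These are counts at randomisation; fewer may enter Epoch 4.

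**3. What can pass the percent flags in both epochs?** Assume that each epoch is flagged against its own baseline and that no intermediate value goes beyond the epoch's end value. With change a in Epoch 3 and b in Epoch 4, the 48-week change is (1 + a)(1 + b) - 1.
- Hemoglobin (criterion: more than 20% decrease): 0.88 × 0.88 - 1 = 0.7744 - 1 = -22.6%. Neither -12% step is flagged.
- Creatinine (criterion: 50% or more increase): 1.30 × 1.20 - 1 = +56%. Neither step is flagged under Table 2-5.

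The bound is f² - 1, with f the threshold as a ratio to baseline. For hemoglobin, 0.8² - 1 = -36%. For creatinine, 1.5² - 1 = +125%, approached but not reached because the criterion includes 50% itself. These show what is possible; they do not predict frequency.

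**4. What is unaffected?** The potassium limits and the absolute limits for sodium, calcium and low glucose in Table 2-5 do not depend on a baseline. The liver criteria in Table 2-7 are multiples of ULN. Table 2-8 has a 25-49% creatinine alert, so the +30% step could be caught as a renal event in Epoch 3, subject to confirmation. Table 2-5 has only percent criteria for hemoglobin, though a value crossing the normal range would still appear in a shift table.

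**The case against.** The Week 24 reference has a purpose. Active-arm subjects change dose at Week 24, and secondary objective 6 asks for laboratory data between Weeks 24 and 48. That stands, so the Week 24-referenced tables should stay.

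A reader might infer that abnormalities arising in Epoch 3 are hidden. The documents do not support this. The Week 24 analysis reports visit changes, maximum change, shifts and notable values from randomisation, and SAP 1.1 puts both analyses in the CSR. An abnormality still present at Week 24 appears as abnormal-to-abnormal in the later shift table.

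A reader might also infer that no laboratory result is referred to randomisation at end of study. That goes too far. The sentence in SAP 2.8.3 contrasts change from Week 24 with maximum change from BL, and using two names suggests two references. Protocol 9.5.2.2 has the same wording under a glossary that fixes BL at Visit 201. Against that, SAP 2.1.1 moves baseline for Epoch 4-only analyses. The text does not settle it, and on the favourable reading there is still only one statistic, with no shift, by-visit or notable-change result.

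Nor does it follow that a two-step rise is never detected. The renal alert, absolute limits and liver criteria remain, and clinically significant laboratory abnormalities are adverse events (Protocol 7.1), which are summarised over 48 weeks. These are partial safeguards and do not replace the laboratory analysis that objective 5 implies.

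**Conclusion.** The point holds as a gap in the planned outputs. No laboratory shift, change-by-visit or Table 2-5 analysis over Weeks 0-48 from randomisation is specified, and the Table 1-1 urinary endpoint at Week 48 has no matching analysis. These two statements rest on the text alone.

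The escape of gradual build-up from Table 2-5 (hemoglobin -22.6%, creatinine +56% in the illustrations) is conditional: it assumes the End of study flags use the SAP 2.1.1 Epoch 4 baseline, which SAP 2.8.3 does not say. How often it would happen cannot be derived from the documents. The meaning of BL in the maximum change is a separate ambiguity. The outputs are descriptive, so no error rate or efficacy conclusion is affected; what suffers is the completeness of the 48-week safety account.

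**What to change.** In SAP 2.8.3:
- Add overall (Weeks 0-48) laboratory tables against the randomisation baseline by the 10 randomised groups, the grouping SAP 2.1.1 already sets for overall analyses: change by visit, maximum change, shift to the most extreme value, and Table 2-5 notable changes.
- Keep the Week 24-referenced tables for objective 6.
- Add change from baseline at Week 48 for urinary calcium and phosphorus, to match Table 1-1.
- State that BL means randomisation for the End of study maximum change and for the overall notable-value listing.

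The data are already scheduled, so the cost is one additional set of descriptive tables.

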1.2 Study objectives and endpoints

Table 1-1 Objectives and related endpoints

Objective	Endpoint	Analysis
Primary objective		
To determine the dose-response signal and assess the dose-response relationship of two dose regimens of LIK066 as measured by the percent change from baseline (BL) in body weight relative to placebo after 24 weeks of treatment	Percent change from BL at Week 24 in body weight	Section 2.5.2
Secondary objectives		
To assess the responder rates according to percent decrease in body weight either $\geq 5\%$ or $\geq 10\%$, from BL at Week 24, for the overall population and each of the subgroups (normoglycemic subjects, dysglycemic subjects, and subjects with T2DM)	Proportion of patients with percent change from BL at Week 24 in body weight: 
 • $\leq -5\%$ • $\leq -10\%$ 	Section 2.7.2.1
To assess the dose-response relationship for weight loss in normoglycemic subjects, dysglycemic subjects and subjects with T2DM after 24 weeks of treatment	Percent change from BL at Week 24 in body weight	Section 2.7.2.1
To evaluate the effect of all LIK066 doses and regimens vs placebo for the overall population	Change from BL at Week 24 in:	Section 2.7.2.1

and by subgroups after 24 weeks of treatment on:
 
• Waist circumference• Change from BL in glycated hemoglobin A1c (HbA1c)• Change from BL in fasting plasma glucose (FPG)• Changes in systolic blood pressure (SBP) and diastolic blood pressure (DBP)• Percent changes in the fasting lipid profile and high sensitivity C-reactive protein (hsCRP)• 24-h urinary glucose excretion (UGE) in a subset of subjects	
• Waist circumference• HbA1c• FPG• SBP and DBP• 24-h UGE 
Percent change from BL at Week 24 in:
 
• Lipid parameters• \log_{10} transformed hsCRP	
To evaluate the change in weight and other efficacy parameters listed above in the overall population by LIK066 treatment vs placebo between Week 24 and Week 48	Change from Week 24 at Week 48 in efficacy parameters listed above	Section 2.7.2.2

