To evaluate safety (adverse events (AEs) and laboratory parameters) and tolerability of LIK066 over 24 weeks of treatment and over 48 weeks of treatment for all subjects	Safety outcomes include: 
• AEs/SAEs• Death• Laboratory data• Vital signs• ECG• Liver events• Renal events• Bone and renal biomarkers	Section 2.8.1 Section 2.8.2 Section 2.8.3 Section 2.8.4 Section 2.8.5 Section 2.8.6 Section 2.8.7 Section 2.12
To evaluate AEs of interest and laboratory data in subjects treated with LIK066 25 mg qd, 35 mg qd or placebo between Week 24 and Week 48 (during Epoch 4)	AE of special interest, diarrhea, ketoacidosis, hypoglycemic event, etc.	Section 2.8.1
To evaluate 24-h urinary calcium and phosphorus excretion after 24 weeks of treatment and after 48 weeks of treatment in a subset of subjects	Change from BL at Week 24 and at Week 48 in the 24-h urinary calcium and phosphorus excretion	Section 2.8.3

To evaluate the pharmacokinetics (PK) of LIK066	
• Concentration• Lapsed time	Section 2.10

2 Statistical methods

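### SAP Table 1-1 defines the Week 48 urinary calcium and phosphorus endpoint as change from baseline, but the end-of-study analysis specifies only change from Week 24

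*SAP*

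**What the plan says.** Protocol 2.2, objective 7, is "To evaluate 24-h urinary calcium and phosphorus excretion after 24 weeks of treatment and after 48 weeks of treatment in a subset of subjects". It names no reference point for the change.

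SAP Table 1-1 supplies one. It gives the endpoint as "Change from BL at Week 24 and at Week 48 in the 24-h urinary calcium and phosphorus excretion" and refers to SAP 2.8.3 for the analysis.

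SAP 2.8.3 has two parts:

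- **Week 24 analysis:** "The change from BL in the 24-h urinary calcium and phosphorus excretion will be descriptively summarized by treatment and visit".
- **End of study analysis:** "The change from Week 24 in the 24-h urinary calcium and phosphorus excretion will be descriptively summarized by treatment and visit", restricted to visits after Week 24.

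Protocol 9.5.2.2 carries the same end-of-study sentence. SAP 2.1.1 limits the first part: "For the Week 24 analyses, data collected up to the end date of Epoch 3 will be included". SAP Section 4, which lists changes from the protocol's analyses, mentions only hsCRP.

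**The concern.** The endpoint is defined against one reference and the end-of-study analysis uses another. For subjects on LIK066 in Epoch 3, Week 24 is not a drug-free value, so change from Week 24 answers a different question: what happened after the switch to the Epoch 4 regimen, not how far excretion stands from its pre-treatment level after 48 weeks.

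What is at stake is the reading of a longer-term safety measure. A rise that developed in Epoch 3 and persisted would appear as roughly no change in the end-of-study table. The group that moved from placebo to 25 mg qd has a drug-free Week 24 value, so its whole drug effect would appear in the same table. Set side by side, the groups with longer exposure could look less affected than the group with shorter exposure simply because their references differ.

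**Working it through.** There is no planned figure to reproduce. The check is whether any planned output yields change from randomisation baseline at Week 48.

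1. **What BL means in the endpoint.** SAP 2.1.1 sets the randomisation baseline for the Week 24 and overall analyses, but adds: "Baseline for End of study analysis including Epoch 4 data only will be defined as the last measurement in Epoch 3". In the Table 1-1 cell a single BL governs both time points, and for the Week 24 part it cannot be the last Epoch 3 value. Where the same table intends Week 24 as the reference it says so: "Change from Week 24 at Week 48 in efficacy parameters listed above". The natural reading is the randomisation baseline.

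2. **Search for an output that delivers it.**
   - SAP 2.8.3, Week 24 analysis: right reference, but Epoch 3 data only.
   - SAP 2.8.3, End of study analysis, and protocol 9.5.2.2: right time point, but change from Week 24.
   - SAP 2.8.3, general laboratory sentence at end of study: "presented by treatment group for each parameter, as well as for the maximum change from BL". A maximum over visits is not the Week 48 change, and Table 2-4 does not list the 24-h urine parameters.
   - SAP 2.1.1, overall analysis over both epochs: a baseline is defined, but no overall analysis of these parameters is specified.
   - SAP 2.12 and protocol 9.5.6, biomarkers: absolute values and change from Week 24, with no change from randomisation baseline at Week 48.

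3. **Can the two change tables be added?** For one subject,

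   (Week 48 − BL) = (Week 24 − BL) + (Week 48 − Week 24).

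   If a rise d at Week 24 is fully maintained, this is d = d + 0, and the end-of-study table shows only the 0. At group level the sum fails because the tables differ in both grouping and membership. The Week 24 table uses nine arms in the safety set; the end-of-study table uses four pooled groups of subjects who entered Epoch 4.

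4. **What the pooled change from Week 24 mixes.** From the planned arm sizes in protocol 5.2, each LIK066 pool has 36 + 36 + 36 + 72 = 180 subjects. In the qd pool, the 50 and 150 mg arms (36 + 72 = 108, or 3/5) go to a lower total daily dose in Epoch 4, and the 2.5 and 10 mg arms (72, or 2/5) to a higher one. In the bid pool, total daily doses are 5, 10, 50 and 100 mg against 35 mg in Epoch 4, giving the same 108 and 72. The pooled mean therefore averages changes that follow opposite dose moves. It could be negative while excretion remains above the pre-treatment level.

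5. **Who is affected.** Protocol 6.6.3.2 plans about 120 substudy subjects. Placebo is 72 of 432, or 1/6. If the substudy mirrors the overall allocation (an assumption), about 120 × 1/6 = 20 are on placebo in Epoch 3 and about 100 on LIK066. The 100 is an upper figure, since those not entering Epoch 4 are outside the end-of-study table.

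6. **Are the data there?** Protocol 6.4.7 measures urinary calcium and phosphate in the same 24-h collection as urinary glucose, and Table 6-1 schedules that collection at randomisation and at the final visit. The endpoint can be computed from data already planned.

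**The case against.** The best case against has four parts.

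**The two-baseline rule in SAP 2.1.1 may reconcile the texts.** If BL at Week 48 means the last Epoch 3 value, Table 1-1 and 2.8.3 agree, and the SAP's document history shows that the rule was deliberate. This does not hold up against the wording of Table 1-1, for the reasons in step 1 of the working. It does show that the SAP should say which baseline applies.

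**The signal is not hidden.** A reader might infer that a maintained rise vanishes from the report. The documents do not support that. The Epoch 3 change from baseline is tabulated by treatment and visit, and SAP 1.1 places both analyses in the CSR. SAP 2.12 covers urine bone biomarkers, which protocol 6.4.7 identifies as calcium and phosphate excretion, so absolute end-of-study values appear to be planned, with a placebo/placebo group beside them. (Table 2-9 lists calcium and phosphates without naming serum or urine.) This stands. What is missing is the within-subject change, not all sight of the level.

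**Not everyone is affected.** A reader might extend the problem to all of the roughly 120 subjects. The masking needs active drug before Week 24, so it does not apply to subjects on placebo in Epoch 3. This stands.

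**The protocol is not self-contradictory.** Objective 7 names no reference point, and change from Week 24 is the usual Epoch 4 convention in both documents. This stands: the conflict is between SAP Table 1-1 and SAP 2.8.3.

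A reader might also suppose that the subset exists to follow up the preclinical calcium and renal mineralisation findings in protocol 3.6. The protocol draws no such link. Section 6.5.6 gives bone re-modelling and possible kidney injury as the reasons for the biomarkers.

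**Conclusion.** The point holds in limited form. The SAP defines a Week 48 endpoint as change from baseline and specifies no output that gives it, and Section 4 does not declare a departure. In the two LIK066/LIK066 groups the table that is planned would show a maintained rise as about zero change, and the other planned tables do not combine to recover the endpoint.

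The size is modest: a descriptive secondary safety endpoint, in at most about 100 substudy subjects under the proportional-allocation assumption, with no bearing on the primary analysis, the type I error or the power. The near-zero reading assumes that the Epoch 3 rise is maintained; a partly reversed rise would show as a fall. The conclusion also rests on reading BL in Table 1-1 as the randomisation baseline, which that table's own wording supports.

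**What to change.** In the End of study analysis of SAP 2.8.3, add a descriptive summary, by treatment, of change from the randomisation baseline (Visit 201) at Week 48 in 24-h urinary calcium and phosphorus excretion, next to the change from Week 24. State in SAP 2.1.1 or Table 1-1 that BL for this endpoint is the randomisation baseline. Align protocol 9.5.2.2 if the protocol is amended for other reasons.

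The cost is one extra descriptive table and one sentence, with no new data collection. If the sponsor does intend change from Week 24 alone, Table 1-1 should be reworded to say so and the reason given.
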